#### **9.2.4 Reporting Requirements for All SAEs**

All SAEs must be reported to Bellicum (via Pharmalex) within 24 hours of learning of the event using the Bellicum SAE Report Form.

For initial SAE reports, investigators should record all case details that can be gathered within the reporting timeframe (24 hours) on the Pharmalex SAE Report Form and submit the report to [REDACTED]

[REDACTED] Follow-up information should be collected on the Pharmalex SAE Report Form as soon as it becomes available.

If local laws require that the site submit all SAEs then the local law will supersede the protocol requirements.

#### **9.2.5 Type and Duration of Follow-Up of Patients after Adverse Events**

The investigator should follow all unresolved AEs and SAEs until the events are resolved or stabilized, the subject is lost to follow up, or it has been determined that the study treatment or participation is not the cause of the AE/SAE. Resolution of AEs and SAEs (with dates) should be documented on the AE Case Report Form (CRF) or eCRF and in the subject's medical record to facilitate source data verification.

For some SAEs, the Sponsor or its designee may follow up with the site by telephone, fax, electronic mail, and/or a monitoring visit to obtain additional case details deemed necessary to appropriately evaluate the SAE report (e.g., hospital discharge summary, consultant report, or autopsy report).

#### **9.2.6 Post-Study Adverse Events**

The investigator should notify the study Sponsor of any death or other SAE occurring at any time after a subject has discontinued or terminated study participation if felt to be related to prior study treatment. The Sponsor should also be notified if the investigator should become aware of the development of cancer or of a congenital anomaly in a subsequently conceived offspring of a

subject that participated in this study. The investigator should report these events to Bellicum on the study CRF or eCRF. If the study CRF or eCRF system is no longer available, the investigator should report the event directly to Bellicum via phone or email

### **9.3 End of Study**

The study will evaluate overall survival and disease-free survival for all patients enrolled at 1 and 2 years post-transplant. Patients will be followed for a total of 15 years after BPX-501 treatment for gene therapy safety events. The study will be closed after the completion of the 15 years of follow-up.

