## 2 SYNOPSIS

Study Identifier(s)	BP-404 EudraCT #2016-003226-16
Aim of the Study	This is a Phase I/II study to evaluate the long-term safety of the infusion of BPX-501 gene-modified T cells after mismatched, T cell-depleted allogeneic transplantation and evaluate disease free survival at 1 and 2 years post-transplant
Study Design	
Open label, multi-centre, non-randomized, non-controlled long-term safety evaluation
 
Follow-up of all patients enrolled on BP-004 and treated with BPX-501 who are beyond Day 180 and have completed or discontinued the parent study.

Study Population	The patient population is identical to BP-004 as it is the long-term follow-up of those patients. Estimated enrolment up to 175 BP-004 patients.
Main Inclusion Criteria	
 
1. Signed written informed consent by the patient or the patient's guardian for children who are minors
 
2. Enrolled on BP-004 protocol, received BPX-501 infusion, completed or discontinued from the study, and are beyond Day 180.
 

Main Exclusion Criteria	
 
1. Lack of parents'/guardian's informed consent for children who are minors
 
2. Withdrawal from BP-004 study prior to BPX-501 infusion.
 

Dosage, Treatment Regimen, Route of Administration	
No BPX-501 infusions will be administered under this protocol.
 
Rimiducid to be given at 0.4 mg/kg weight (intravenous infusion) only in the setting of uncontrolled GVHD.

Locations (e.g. regions)	Italy, Saudi Arabia.
Primary Endpoint(s) with Time Point(s) of Assessment	Overall Survival and incidence of Disease-Free Survival in both malignant and non-malignant patients at 1 year and 2 years post-transplant. Relapse-Free Survival in malignant patients at 1 year and 2 years post-transplant.
Main Secondary Endpoint(s) with Time(s) of Assessment	Long-term safety for a total of 15 years from BPX-501 administration

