**Table 1: Schedule of Events (Laboratory and Clinical)**

Time - Months (+/- 14 Days)	9	12	15	18	21	24	30	36	42	48	54	60	YEARLY	6-15
Overall Survival (OS)		X				X		X		X		X		X
Disease-Free Survival (DFS)		X				X		X		X		X		X
Relapse-Free Survival (RFS)		X				X		X		X		X		X
Hematology; Chemistry	X	X	X	X	X	X								
Immune Reconstitution  :	X	X	X	X	X	X								
RCR 	X	X	X	X	X	X	X	X	X	X	X	X		X
Modified History & Physical	X	X	X	X	X	X	X	X	X	X	X	X		X
Neurological Exam 	X	X	X	X	X	X	X	X	X	X	X	X		X
Vital Signs 	X	X	X	X	X	X								
GVHD Assessment 	X	X	X	X	X	X								
Concomitant Medication 	X	X	X	X	X	X								
Adverse Event	X	X	X	X	X	X	X	X	X	X	X	X		X
Bellicum Research Samples	BPX-501 T cell Assessment Research samples for assessment of BPX-501 cells (CD3+CD19+) will be collected monthly ( $\pm$ 14 days) until 1-year post BPX-501 infusion, every 6 months ( $\pm$ 1 month) for 24-months post BPX-501 infusion.													
	Post-systemic corticosteroid administration: Research samples (peripheral blood and/or tissue) for assessment of BPX-501 cells (CD3+CD19+) will be collected and sent to the sponsor prior to administration of systemic corticosteroids doses (e.g. methylprednisolone), at 4-hours ( $\pm$ 30 minutes) and 24-hours ( $\pm$ 1 hour) post-systemic corticosteroid initiation, and at 7-days, 14-days, 21-days, and 28-days ( $\pm$ 24 hours) post-systemic corticosteroid initiation.													
Rimiducid Infusion 	BPX-501 Cellular Kinetics (post-rimiducid) Within 4 hours ( $\pm$ 30 minutes) prior to initiation of rimiducid infusion, 30 minutes ( $\pm$ 5 minutes), then at 2 hours, 4 hours, 6 hours, 8 hours, 12 hours, and 24 hours ( $\pm$ 30 minutes) after initiation of infusion (of each dose of rimiducid) samples will be collected (and will be split for separate processing). Subsequently at 48 hours ( $\pm$ 1 hour) and 7 days (after initiation of infusion of each dose of rimiducid), and then at 14 days, 21 days, and 28 days ( $\pm$ 24 hours) after the final dose of rimiducid (if more than one dose is administered) blood samples will be drawn and evaluated for T cell responses only.													

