#### **5.4 Subject Inclusion Criteria**

1. Signed written informed consent by the patient or the patient's guardian for children who are minors.

2. Enrolled on BP-004 protocol, received BPX-501 infusion, completed or discontinued from the study, and are beyond Day +180.

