## 7.3 Patient Enrollment, Registration and Assignment to Treatment

Informed consent will be obtained from each patient and/or parent or guardian after the nature of the study is explained and prior to the performance of any study-specific procedures.

Upon enrollment into the study, the patient will continue with the same number assignment as assigned in BP-004.

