## **10.4 Statistical Methods**

### **10.4.1 Sample Size Determination**

The sample size is identical to BP-004 as it is the long term follow-up of those patients.

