#### **10.4.5 Endpoint Analysis**

##### **10.4.5.1 Analysis of Overall Survival**

Overall survival, measured as the period of time from the start of the treatment that the patients are still alive at 1 year and 2 years post-transplant will be assessed and reported.

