6.2.3. Baseline Definition

For this study, the patient begins study treatment on the day of hematopoietic stem cell transplantation (HSCT) defined as Day 0 in the protocol and study Day 1 for analysis. It is noted that the study schedule from the protocol refers to the reference date as Day 0. For reporting purposes, CDISC standards will be used, referring to the first day as Day 1.

If a patient received multiple HSCTs, the date of HSCT which occurred immediately before administration of BPX-501 will be considered study Day 1.

For all endpoints requiring a baseline reference, e.g., comparison with a post-baseline value, the baseline value will be the last non-missing result prior to HSCT.

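### Protocol 9.3 evaluates 1- and 2-year post-transplant survival in enrolled patients, who must be alive beyond Day 180 to enrol, and the SAP uses a different set

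*Protocol*

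**What the plan says.** BP-404 is the long-term follow-up of BP-004. Its primary objective (Protocol 5.1) is OS and disease-free survival (DFS) in both disease groups, and relapse-free survival (RFS) in malignant disease, at 1 and 2 years after transplant. Protocol 9.3 says whose survival is evaluated: "The study will evaluate overall survival and disease-free survival for all patients enrolled at 1 and 2 years post-transplant".

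The entry condition is in Protocol 5.4: "Enrolled on BP-004 protocol, received BPX-501 infusion, completed or discontinued from the study, and are beyond Day +180". No latest entry date is given. Protocol 7.3 adds: "Informed consent will be obtained from each patient and/or parent or guardian after the nature of the study is explained". The OS clock is in Protocol 10.4.5.1: "Overall survival, measured as the period of time from the start of the treatment". The SAP fixes that starting point in 6.2.3: "the patient begins study treatment on the day of hematopoietic stem cell transplantation (HSCT) defined as Day 0 in the protocol".

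Other protocol text points towards the whole parent cohort. The Synopsis says "The patient population is identical to BP-004 as it is the long-term follow-up of those patients", and 10.4.1 says "The sample size is identical to BP-004 as it is the long term follow-up of those patients". Section 10.4.2 refers to an overall population without defining it. Section 10.4.5.4 counts leukaemia relapse from the day of transplant, with earlier death as a competing risk.

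The SAP (6.7) estimates OS, DFS and RFS from HSCT by Kaplan-Meier at 180 days, 1 year and 2 years in the ITT population. SAP 6.1 equates this with the full analysis set (FAS): transplanted patients given BPX-501 at 1×10^6 cells/kg. SAP 6.7 describes these analyses as additions that the protocol did not specify. SAP section 2 says that the plan is based on BP-004, may draw on BP-404 data beyond Day 180, and takes precedence over the protocols where they differ.

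**The concern.** A patient who died on Day 100 cannot be consented into BP-404 and so cannot be among its enrollees. If the clock starts at transplant for those who did enrol, each of them carries at least 180 days in which death was ruled out by selection. This is immortal time.

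BP-404 is uncontrolled and descriptive (Protocol 2 and 10.4.2), so no test is affected. The survival percentages are the main result, and a reader will take 2-year post-transplant survival to mean the chance of survival counted from transplant. An enrollee-only figure is more favourable than that. Since the SAP names another set, two different numbers could also be reported under the same endpoint name.

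**Working it through.** The documents contain no OS estimate and no precision calculation for BP-404, so there is no stated figure to reproduce. The check compares the passages and then sizes the effect under assumptions. Day 180 is taken as counted from transplant.

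**Who can contribute under 9.3.** Entry requires BPX-501 infusion on BP-004, new consent, and being past Day 180. Every enrollee is therefore alive at some time e later than Day 180. The clock starts earlier than e, whether the start of treatment means transplant or infusion.

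**Whether the protocol repairs this.** Sections 10.4.1 to 10.4.6 contain no delayed-entry or landmark rule and no instruction to add BP-004 deaths. Linking enrollees' own BP-004 histories would not restore patients who died before they could enrol.

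**Size for OS.** If everyone enters at Day 180, and consent among the living is unrelated to prognosis:

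enrollee-only OS(t) = OS(t) / S(180)

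For entry at a later time e, the divisor is S(e), which is no larger than S(180), so 1/S(180) is a lower bound on the factor. A patient who enters after 1 year is a certain 1-year survivor.

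S(180) and true OS are both assumed below. The factors are 1/0.98 = 1.020 and 1/0.95 = 1.053.

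| Time | Assumed true OS | S(180) = 0.98 | S(180) = 0.95 |
|---|---|---|---|
| 1 year | 80% | 0.80/0.98 = 81.6% (+1.6) | 0.80/0.95 = 84.2% (+4.2) |
| 1 year | 90% | 0.90/0.98 = 91.8% (+1.8) | 0.90/0.95 = 94.7% (+4.7) |
| 2 years | 75% | 0.75/0.98 = 76.5% (+1.5) | 0.75/0.95 = 78.9% (+3.9) |
| 2 years | 85% | 0.85/0.98 = 86.7% (+1.7) | 0.85/0.95 = 89.5% (+4.5) |

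If 175 patients were infused (the planned maximum), the deaths left out would number 175 × 0.02 = 3.5 to 175 × 0.05 = 8.75, or about 4 to 9.

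**DFS and RFS.** The formula does not carry over. A patient who relapsed before Day 180 but is alive may enrol, so selection is on being alive and not on being event-free. Early deaths are still lost, but the size of the bias differs and cannot be derived from S(180) alone.

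**The SAP's set.** The FAS has no Day-180 condition, so this source of bias is absent. It is not free of all conditioning. SAP 4.1 puts infusion at Day 14 ± 4, or Day 21 ± 14 under some versions, and membership requires surviving to infusion. It is also narrower than BP-404. Protocol 5.4 admits any BPX-501 recipient, and Protocol 7.2 lists dose levels from 2.5×10^5 to 4×10^6 cells/kg. The SAP's outputs for 1×10^6 cells/kg or above (7.1.1) cover RFS but not OS.

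**The case against.** The best defence is that the only statistical plan supplied already does the right thing. It times OS, DFS and RFS from HSCT, sets no Day-180 condition, and claims precedence. On that view the overstatement arises only if the SAP is ignored, and 9.3 is a closure paragraph rather than a definition of an analysis set. The statements that the population and sample size match BP-004, and the relapse analysis from transplant, suggest that linked parent-study data were intended.

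Much of this stands as mitigation. It does not settle the matter. The SAP was written for BP-004, treats the BP-404 primary endpoints as additional exploratory analyses, and reports no major change from the protocol (SAP 6.6), so the conflict is never acknowledged. The statement that the population is identical cannot hold literally if patients who died before entry cannot enrol. Where the protocol means the parent study it usually says so (5.4, 7.2), and 9.3 does not. A separate BP-404 SAP may exist but is not among the documents.

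A reader might infer more than the documents support:

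- That reported survival is in fact biased. Nothing shows which set was used.
- That all deaths before the month-9 visit in Table 1 must come from BP-004 data. Events are reported from BP-404 consent (Protocol 9.1.4) and survival status is followed (6.1), so a death between consent and month 9 can be captured on BP-404.
- That the 91% in SAP 4.2 gives Day-180 survival. It is an event-free survival planning value that also counts GvHD and Grade 4 infection.
- That patients entered after 1 year. Protocol 5.4 permits it, but nothing shows that it happened.

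The SAP's inclusion of UK patients and its use of the name DFS only for non-malignant disease are side issues.

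**Conclusion.** Section 9.3 is wrong as written. Applied literally, it gives survival conditional on being alive at BP-404 entry under a post-transplant label. If anyone died before Day 180, OS is overstated by a factor of at least 1/S(180), provided that consent among survivors is unrelated to prognosis. The size is illustrative only: 2% to 5% dead by Day 180 would add about 1.6 to 4.7 points to a true 1-year OS of 80% to 90%. No comparable figure can be given for DFS or RFS.

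The SAP removes the Day-180 condition but restricts the set to one dose level and is still conditional on surviving to infusion. The documents therefore leave two different sets for the same primary endpoint. The point should be fixed. It concerns the definition and label of the main estimate and does not show that any result is biased.

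**What to change.** In Protocol 9.3 and 10.4.5, replace the reference to enrolled patients, for OS, DFS and RFS, with text along these lines:

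- The analysis set is all patients infused with BPX-501 under the BP-004 protocol version or versions that feed BP-404, with those versions named.
- Time runs from HSCT and is analysed by Kaplan-Meier with entry into the risk set at BPX-501 infusion. Otherwise the result is labelled as conditional on surviving to infusion.
- Deaths and relapses recorded on BP-004 are linked through the subject number, which Protocol 7.3 carries over.
- Infused patients who did not enrol on BP-404 are censored at last contact.
- The SAP's 1×10^6 cells/kg FAS is reported as a defined subset.
- Any enrollee-only estimate uses delayed entry at the enrolment date and is labelled as conditional on survival to entry.

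The cost is a wording change, a little data linkage, and a somewhat less favourable survival figure than the enrollee-only one. Censoring non-enrollees at last contact assumes that not enrolling is unrelated to prognosis. Their number and last-contact times should be reported so that a reader can judge this.

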## **10 DATA COLLECTION, QUALITY ASSURANCE AND MANAGEMENT**

### **10.1 Recording of Data**

Data will be recorded on an electronic database and will be entered after validation into a computer system for subsequent tabulation and analyses. The investigator must ensure that each subject's anonymity is maintained. Patients will be identified by a unique subject identification number. Study related documents should be kept in strict confidence by the investigator in compliance with applicable regulations and ICH Good Clinical Practice (GCP) Guidelines.

### **10.2 Data Quality Assurance**

The investigators undertake to perform the study in accordance with this protocol, GCP and the applicable regulatory requirements.

The investigators are required to ensure compliance with the investigational product schedule, visits schedule and procedures required by the protocol.

The investigators agree to provide all information requested in the Case Report Form in an accurate and legible manner.

### **10.3 Data Management**

The investigator will fill in eCRF for documentation. All relevant data collected during the study for all of the patients enrolled into the study have to be entered into the database by the responsible investigator or someone authorized by him/her in a timely manner. The principal investigator (PI) will review all the eCRFs of each patient and confirm the completeness, medical correctness and plausibility of the documented data by signing on all eCRF pages.

Additions and corrections in the eCRF will be dated and signed by the responsible investigator or an authorized person. Reasons must be given for corrections that are not self-explanatory.

Bellicum or the Contract Research Organization (CRO) will ensure that the clinical trial is conducted, recorded, and reported in accordance with the protocol, ICH-GCP, and the applicable regulatory requirement(s).

Representatives of Bellicum or the CRO must be allowed to visit all study site locations periodically to assess the data, quality and study integrity. On-site they will review study records and directly compare them with source documents and discuss the conduct of the study with the investigator, and verify that the facilities remain acceptable. Source documents are defined as: patient files, letters, and laboratory/histology records.

## **10.4 Statistical Methods**

### **10.4.1 Sample Size Determination**

The sample size is identical to BP-004 as it is the long term follow-up of those patients.

### **10.4.2 General Statistical Approach**

Descriptive statistics will be utilized to summarize overall survival, RFS, DFS, GvHD rates, clinical and biologic response and other measures of safety and toxicity in those patients who received rimiducid administration as well as for the whole population. The analysis population will be stratified by malignant and non-malignant indications.

Data per cohort will be presented, stratified according to the type of disorder, e.g. malignant or non-malignant.

All summary tables for quantitative parameters will display mean, standard deviation, median, range (minimum and maximum), as well as number of missing data, where relevant. All summary tables for qualitative parameters will display counts, percentages, and, number of missing data, where relevant.

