### **5 OBJECTIVES OF THE STUDY**

#### **5.1 Primary Objective**

Overall Survival and incidence of Disease-Free Survival in both malignant and non-malignant patients at 1 and 2 years post-transplant. Relapse-Free Survival in malignant patients at 1 year and 2 years post-transplant.

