## **7 DESIGN AND CONDUCT OF THE STUDY**

### **7.1 Trial Rationale**

This is a long-term follow-up study evaluating the safety of BPX-501 T cells infused after partially matched, related, T cell-depleted HSCT in pediatric patients previously enrolled on the BP-004 protocol who received BPX-501, completed or discontinued from the study and are beyond Day 180. The trial will evaluate the treatment of GvHD by the infusion of dimerizer drug (rimiducid) in those patients who present with cGvHD who progress or do not respond to standard of care treatment.

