### **7.5 Infusion of Rimiducid**

#### **7.5.1 Chronic GVHD Treatment**

Chronic GVHD (cGVHD) typically occurs 100 days or later after HSCT. cGVHD can often present with a sicca-like syndrome with thickened skin, lichen planus, papules, cholestatic jaundice, scleroderma-like skin, eye and GI lesions. cGVHD patients can also develop obstructive pulmonary disease symptoms.

cGVHD is typically classified into mild (i.e., localized skin involvement, with/or without liver dysfunction) or moderate to severe (i.e., generalized skin involvement or localized skin and/or hepatic dysfunction, plus liver histology showing hepatitis/necrosis/cirrhosis, eye involvement, salivary gland involvement, or effects on other organs). Moderate to severe cGVHD usually involves more than one organ with an organ severity score of moderate or greater (or mild or greater for lungs). Management guidelines for cGVHD are shown in [Appendix B](#).

Response should be assessed per [Appendix B](#). Three general categories of overall response are used in clinical trials: complete response (CR), partial response (PR), and lack of response (unchanged, mixed response, progression). Complete response is defined as resolution of all manifestations in each organ or site, and partial response is defined as improvement in at least 1 organ or site without progression in any other organ or site. The 2014 NIH Consensus Working Group recommends that skin, mouth, liver, upper and lower GI, esophagus, lung, eye, and

joint/fascia be considered in evaluating overall response. Genital tract and other manifestations are not included due to lack of validated response measures.

Partial response in a specific organ requires an improvement of 1 or more points on a 4 to 7-point scale or an improvement of 2 or more points on a 10 to 12-point scale. The overall category of PR requires the absence of progression in any organ.

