3.2. Study Endpoint(s)

Endpoints will be further defined in subsequent sections. Unless otherwise specified, time-to-event endpoints will be calculated from the date of HSC infusion. If a patient received more than one HSCT, the time of the last HSC infusion immediately preceding infusion with BPX-501 will be the transplant date.

Primary Endpoint:

Event-Free Survival (EFS) at 180 days. Events are defined as the first occurrence of either transplant-related mortality (TRM) for non-malignant patients or non-relapse mortality (NRM) for malignant patients, severe GvHD (Grade 2-4 acute organ GvHD or extensive/moderate-severe chronic GVHD), and life-threatening infections (Grade 4).

NB: In the BPX-501 protocols, the terminology 'extensive' chronic GvHD was used. For the purposes of the primary analysis and for the rest of this SAP, extensive chronic GvHD will be defined as moderate or severe chronic GvHD. 'Overall' chronic GvHD or chronic GvHD without a qualifier will be interpreted as mild, moderate or severe chronic GvHD.

The following secondary endpoints are in the BP-004 protocols, although additional endpoints and analyses are described below in subsequent sections of this document.

Secondary Endpoints:

- (i) Transplant-Related Mortality (TRM) in patients with non-malignant diagnoses or Non-Relapse Mortality (NRM) in patients with malignant diagnoses at 100 and 180 days
- (ii) Cumulative incidence and severity of acute GvHD (any Grade 2-4 or Grade 3-4) as well as overall and moderate-severe chronic GvHD at 180 days.
- (iii) Time to resolution of acute GvHD after administration of rimiducid
- (iv) Immune reconstitution as determined by T cell subsets up through 180 days
 - a. Absolute CD3 count
 - b. Absolute CD4 count

- c. Absolute CD8 count
- (v) Time-to-immune reconstitution defined by CD3 count > 500 cells/uL; CD4 count > 200 cells/uL; CD8 count of 200 cells/uL
- (vi) Disease-Free/chronic GvHD Survival (DFGS) defined as the first of either disease recurrence, death from any cause, or chronic GVHD
- (vii) Disease status within the following disease indications at 180 days:
 - a. Primary immune disorders as determined by CD3 T cell count ≥ 500 cells/uL and normal levels of IgA and IgM
 - b. Haemoglobinopathies as determined by incidence of RBC transfusion independence for 8 consecutive weeks and untransfused haemoglobin of ≥ 8.5 g/dL

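### Survival of rimiducid recipients, read at 1 and 2 years post-transplant, includes guaranteed time up to the first dose and is biased upward

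*Protocol*

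**What the plan says.** Protocol 10.4.2 opens its plan with "Descriptive statistics will be utilized to summarize overall survival, RFS, DFS, GvHD rates" and other measures, to be shown "in those patients who received rimiducid administration as well as for the whole population". Protocol 5.1 sets the primary objective as "Overall Survival and incidence of Disease-Free Survival in both malignant and non-malignant patients at 1 and 2 years post-transplant", with RFS in malignant patients at the same times. Protocol 10.4.5.1 counts OS from an undefined start of treatment, but still reports at 1 and 2 years post-transplant. In the SAP (3.2), "time-to-event endpoints will be calculated from the date of HSC infusion" unless otherwise specified.

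Rimiducid comes later. Protocol 7.1 describes its use "in those patients who present with cGvHD who progress or do not respond to standard of care treatment", and Protocol 7.5.1 says chronic GVHD "typically occurs 100 days or later after HSCT". SAP 4.1 shows that it could also be given in BP-004 for uncontrolled acute GvHD. Follow-up lasts 15 years after BPX-501 (Protocol 7.2).

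Neither document gives a landmark, delayed entry, a time-dependent treatment state or a dose-based survival clock for recipients. The only clock that runs from infusion of the respective treatment is for the safety analysis (Protocol 10.4.6).

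**The concern.** The recipient group is defined by something that happens after time zero, while survival is counted from time zero. A child who dies before needing rimiducid cannot enter the group. A child first dosed in year 3 enters it as a certain survivor at both 1 and 2 years. This is guaranteed (immortal) time, and the plan does nothing to remove it.

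The recipient figures will stand beside whole-population figures for the primary endpoints, in a trial that says it will evaluate rimiducid treatment of GvHD. Two misreadings are possible. If recipients have the same underlying mortality as everyone else, they will appear to do better. If they have higher mortality, which is plausible in a group selected for refractory GvHD, the bias can hide it. In a long-term safety study the second error matters as much as the first.

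**Working it through.** 10.4.2 states no rate, N or power, so there is no figure to reproduce. The size has to be illustrated under assumptions.

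**From the documents.** Time points are 12 and 24 months post-transplant. All BP-404 patients are beyond Day 180 (Protocol 5.4 and 7.2), taken here as month 6.

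**Assumed, not in the documents.** 2-year OS from transplant is S(24) = 0.80. The planned first dose is uniform over months 6 to 24 and is given only if the patient is alive. Rimiducid has no effect on survival. Two hazard shapes are used:
- A, front-loaded: S(6) = 0.88, constant hazard from month 6 to 24, so S(12) = 0.88 × (0.80/0.88)^(1/3) = 0.852.
- B, constant hazard from transplant: S(6) = 0.80^(1/4) = 0.946, S(12) = 0.80^(1/2) = 0.894.

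**Formulas.**
- Whole BP-404 cohort: S(24)/S(6) at 2 years and S(12)/S(6) at 1 year.
- Recipients at 2 years: S(24) / [mean of S(t) over months 6–24].
- Recipients at 1 year: [6 × S(12) + ∫S(t)dt over months 12–24] / [∫S(t)dt over months 6–24]. Anyone first dosed after month 12 counts as alive at month 12.

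**Results.**

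| | Cohort | Recipients | Artificial gap |
|---|---|---|---|
| A, 2 years | 0.80/0.88 = 90.9% | 0.80/0.8394 = 95.3% | 4.4 points |
| B, 2 years | 0.80/0.946 = 84.6% | 0.80/0.8708 = 91.9% | 7.3 points |
| A, 1 year | 0.852/0.88 = 96.9% | (5.115 + 9.912)/15.109 = 99.5% | 2.6 points |
| B, 1 year | 0.894/0.946 = 94.6% | (5.367 + 10.156)/15.675 = 99.0% | about 4.5 points |

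**Sensitivity.** A simulation used constant hazard, no drug effect, everyone conditioned on survival to Day 180 and 1,000,000 patients per scenario. It gave these gaps for assumed 2-year OS of 90% / 80% / 70%:

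| First dose | Gap at 1 year (points) | Gap at 2 years (points) |
|---|---|---|
| Day 30–180 | 0 / 0 / 0 | 0 / 0 / 0 |
| Day 180–365 | 1.3 / 2.7 / 4.2 | 1.2 / 2.4 / 3.5 |
| Day 180–730 | 2.2 / 4.5 / 7.0 | 3.7 / 7.3 / 10.7 |
| Day 180 to year 15 | 2.6 / 5.3 / 8.2 | 7.1 / 13.9 / 20.3 |

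**Masking.** Now suppose mortality doubles after the first dose, with dosing on Day 180–730, 2-year OS of 80% and the comparator held at the baseline hazard. The 2-year gap is 0.0 points (84.5% in both). At 1 year recipients still look 3.6 points better (98.1% against 94.5%). A true doubling of hazard would not show.

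**The case against.** **The SAP plans no such table.** This is true. SAP 6.7 estimates OS, DFS and RFS in the ITT and possibly the PP population, with OS also split by disease type, and outputs 14.2.13.x have no rimiducid split. The SAP also supersedes the protocols where it differs (SAP 2). But it is silent on this summary, and silence does not withdraw a summary that the BP-404 protocol commits to. The SAP also defines a Rimiducid Population (6.1) and leaves exploratory subgroups open until final analysis (6.7). The objection lowers the priority but does not remove the point.

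**The summaries are descriptive, with no test between groups.** This also stands. It means no formal error rate is affected; a descriptive figure can still mislead.

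**Many doses may be early, and late first doses may be rare.** Doses given in BP-004 before Day 180 add no gap, and scheduled GVHD assessments stop at month 24 (Protocol Table 1). The actual effect could therefore be small. The documents do not allow anyone to say.

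Some stronger readings are tempting but unsupported:
- A reader might compare the 95% under A with the assumed 80% and infer 15 points. That sets recipients against a cohort followed from transplant, whereas BP-404 enrols only patients beyond Day 180.
- A reader might infer that relapse-free time before the dose is guaranteed too. Protocol 6.1 keeps relapsed patients on study, and nothing makes rimiducid conditional on being relapse-free.
- A reader might infer that recipients are bound to look as good as the whole cohort or better. They are selected for refractory GvHD, and a high enough hazard would put them below it.
- A high GvHD rate among recipients is self-evident, since GvHD is the main indication. Response and resolution after rimiducid are already planned (Protocol 10.4.5.3; SAP 6.4.2).

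**Conclusion.** The point holds in a limited form. As written, 10.4.2 produces OS for rimiducid recipients, and RFS and DFS through their death component, that is biased upward relative to a valid estimate. The direction follows from the design; the size does not. The 4 to 7 points at 2 years and 3 to 5 at 1 year rest on 2-year OS of 80%, first doses spread evenly over months 6 to 24, and no drug effect. They grow if first doses after year 2 are counted and vanish for doses before Day 180.

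The whole-population primary estimates do not depend on this sentence, and what is at risk is interpretation. I would ask for the correction but would not treat it as a condition for proceeding.

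**What to change.** In Protocol 10.4.2, take rimiducid recipients out of the post-transplant OS, RFS and DFS summaries. Report their OS, RFS and DFS from the date of first rimiducid dose, for example at 6 and 12 months after dose, with RFS and DFS restricted to patients free of relapse or recurrence at that dose. Repeat the rule in the SAP. For patients first dosed in BP-004, also allow for entry to BP-404 after Day 180: either include every BP-004 recipient from the dose, or use delayed entry at BP-404 enrolment.

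If the transplant clock is kept, use delayed entry at first dose, or a landmark that fixes recipient status and counts follow-up from the landmark. With a valid clock the artificial gap under no effect is zero by construction.

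The cost is a short protocol and SAP amendment and a changed time origin in one set of tables; delayed entry or a landmark needs somewhat more programming. The dates should already be available, since listings of rimiducid administration and of OS, DFS and RFS are planned. The downside is that the recipient figures become less favourable and no longer share a clock with the whole-population figures, so the tables should say so.
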